6.2. Exclusion criteria (both WP)

- Inability to give consent
- Previous Rituximab treatment (ever)
- Chemotherapy with preceding 6 months
- Cystic fibrosis
- Pregnancy
- Breast feeding
- Known current COVID infection/TB infection

7. Study design

This is a single visit study:

Study Procedure	Visit 1
Informed Consent	X
Confirmation meets	X
Inclusion/Exclusion Criteria	
Demographics	X
Medical History	X
Collection in saline of residual tissue	X
removed during clinical procedure	
Sample Processing	X (Processing as per WP)

Table 1: Schedule of Events

(WP1) In Vitro WP:

For *in vitro* experiments, airway tissue will be collected from patients undergoing clinically-indicated resection of nasal polyps and tonsils, dissociated, and B cells separated by magnetic or flow-cytometric isolation. The B cells will then be cultured *in vitro* both with and without stimulation, with and without the presence/absence of recombinant IL-5, Mepolizumab anti-IL-5 antibody, and relevant permutations of cell culture conditions:

Stimulations: unstimulated, anti-CD40 pan B cell stimulation, Staphylococcal enterotoxins (SEA, SEB, SED, SEE), Covid antigens

B cell phenotype after culture will be examined by flow cytometry, secreted antibody measurements by ELISA (including measurement of different subclasses), and bulk antibody repertoire sequencing conducted with BCR-specific primers.

Peripheral blood (20 mls) will also be collected as on optional additional activity preoperatively on the day of surgery. Serum and peripheral blood mononuclear cells will be separated on day of collection. Serum will be stored frozen for future antibody and circulating cytokine ELISA experiments. Peripheral blood mononuclear cells will be stored for future use in analysis of peripheral blood B cell BCR transcriptome and B cell stimulation assays, to probe mechanistic aspects of the research question.

At selected sites we will optionally sample immune mediators (e.g. cytokines) in nasal secretions by nasoabsorption pre-operatively. Secretions will be collected by centrifugation of sponges through a microfilter and frozen at -80°C. Immune mediators (in particular IL-5) will be measured using multiplexed immunoassays (e.g. Luminex) and compared to BCR transcriptome.

These experiments will be used to refine methodology for WP2.

(WP2) Ex Vivo WP:

Nasal tissue will be collected from patients with nasal polyps not on biologics (n=6), with polyps on anti-IL-5(R) biologics (n=6) and control patients without nasal polyposis (n=6) undergoing clinically-indicated nasal surgery. Samples will be dissociated, and cells labelled with oligonucleotide-barcoded antibodies to CD20 and IL-5Ra. Single-cell B cell receptor (BCR) sequencing will be undertaken in the QMUL Core Genomics facility, and BCR repertoire (i.e. immunoglobulin repertoire) analysed to identify the immunoglobulin class, subclass and antibody sequence of tissue B cells from the three patient groups, stratified by IL-5Ra expression. Complementary bulk RNA sequencing with BCR-specific primers will be conducted to increase the depth of sequencing and enable further comparisons between groups.

These samples may additionally be examined by bulk RNA BCR sequencing after *in vitro* stimulation as per WP1. Optional collection of blood and nasoabsorption samples will be conducted at selected sites similar to WP1.

8. Study procedures

Invitation to Participate:

Invitation to Participate will be by members of the clinical team who will provide potential participants with a copy of the Participant Information Sheet (PIS) in advance of their scheduled surgery.

Patients will be identified by participating respiratory clinical teams, from those attending severe asthma services and undergoing nasal surgery as part of their comprehensive airways management, Additional patients will be identified by participating ENT teams, from those attending for surgery for nasal polyps, turbinectomy and septoplasties and reconstructive surgery.

Informed Consent Procedures and Screening:

On the day of scheduled surgery, potential participants interested in the study will be given the opportunity to ask questions from a GCP-trained member of the research team who may or may not be a member of the clinical team treating the participant. After questions have been answered potential participants will be asked to complete the written Informed Consent. Consenting participants will then be briefly screened to check they fulfil inclusion/exclusion criteria.

Data Collection (CRF):

A member of the site clinical team will complete the case report form (CRF) which contains only anonymised information but with a study code to link to patient samples (and to Consent Form for governance purposes). See Source Data section.

Sample Collection:

Excess nasal tissue will be resected by the ENT surgeons and placed in an appropriate container containing a buffered saline solution. Within two hours following the surgery, a member of the research team will collect the samples and transport them securely to the laboratory site adjacent to The Royal London Hospital (Blizard Institute, Barts and The London Medical School, Queen Mary University of London, [name]).

Peripheral venous blood will be collected (optional) with standard aseptic technique. Nasal sections will be collected by nasoabsorption (optional) using nasal sponges placed into each nasal cavity for 5 minutes.

Subject Withdrawal:

In the event that a participant asks to withdraw from the study before the end of the Study Visit then the CRF and samples will be securely destroyed and no recording / analysis of data from that patient undertaken. In the event a participant asks to withdraw from the study after the first Study Visit has been completed the research team will be asked to withdraw any unreported linked data from that participant from the study.

End of Study Definition:

The end of the study is at completion of sample laboratory analysis for the last participant recruited. Statistical analysis of data may continue after the End of Study.

9. Statistical considerations

Associations and comparisons will be analysed with parametric and non-parametric statistical tests as appropriate. Diagnosed health conditions, presence/absence of infection, clinical markers of inflammation, and research laboratory immunological parameters will be analysed as variables likely to interact. Age and gender may also be considered.

As a laboratory research study with aim of revealing hypothesis-generating associations a formal power calculation is not possible. The sample size is based on previous experience with similar projects and feasibility.

10. Ethics

The Chief Investigator will ensure that the study is carried out in accordance with the ethical principles of the Research Governance Framework for Health and Social Care (Second Edition, 2005) and its subsequent amendments as applicable, as well as applicable legal and regulatory requirements. Study approval will include HRA and NHS REC approval, and they study will be conducted in accordance with GCP and declaration of Helsinki.

The research team has no financial or other competing interests for this study.

Human genome (gDNA) analysis will not be conducted as part of this research project.

Clinically defined immunodeficiencies will not be tested for as part of the immunological analyses.

The CRF and samples for immunological analysis will be anonymised so donors are not known to the research team or anyone reviewing the analyses and results.

Invitation to participate will be carried out in advance of scheduled surgery. Informed consent will be undertaken on the day of scheduled surgery. Potential participants will be given as long as they require to ask questions before deciding whether to participate. The study clinical procedure carries minimal risk. Donor decisions to participate or not in the study will not affect their health or clinical care. We therefore feel a short period for informed consent is appropriate for this low-risk study. Requiring potential volunteers to come back on a second occasion to give informed consent and samples would not facilitate ethical recruitment of patients, some of whom need to

travel significant distances for NHS appointments and some of whom have significant chronic ill health.

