4.1. Background

The overlapping conditions of severe asthma, nasal polyps and EGPA are all characterised by chronic eosinophilic airways inflammation. This has led to the successful development of monoclonal antibody treatments that target the primary cytokine for eosinophilic inflammation, interleukin-5 (IL-5). However the receptor for IL-5 is also expressed by other cell types and of note IL-5 was first named as a 'B cell growth factor'. Anti-IL-5 monoclonal antibody therapy may therefore have clinical action through effects on other cell types other than just eosinophils and potentially much of the beneficial effect of blocking IL-5 may be due to the effects on these other cell types. This hypothesis is supported by the excellent response of nasal polyps in clinical trials to anti-IL-5 Mepolizumab but poor clinical response to the eosinophildepleting Dexpramipexole [Laidlaw et al. 2019], and relatively weaker effect of eosinophil-depleting Benralizumab than other biologics in nasal polyp disease [Cai et al. 2022]. The expression of IL-5Ra on other cell types than just eosinophils may also influence safety considerations for Benralizumab (that targets IL-5Ra expressing cells for cell-mediated killing) as compared to biologics that block the cytokine itself. We therefore ask the question – Do IL-5 expressing B cells rather than eosinophils drive chronic rhinosinusitis with nasal polyps and associated eosinophilic airway diseases [Kariyawasam and [name], 2021]?

This is an important question as it would have an impact on the current debate over which of suppression of IL-5 (as seen with Mepolizumab) or depletion of IL-5R expressing cells (Benralizumab) is more effective and which safer – in particular depletion of IL-5R expression B cells may theoretically predispose to specific antibody deficiencies and thereby infection, or other perturbations of healthy human immunity.

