Activation of B cells outside of secondary lymphoid organ germinal centres occurs in peripheral sites such as nasal polyps, under mechanisms controlled by the local peripheral tissue environment [Feldman et al. 2017]. Importantly extrafollicular B cell activation can bypass usual negative selection pressures and thereby is potentially more prone to lead to auto-antibody formation. B cells can respond to IL-5 in terms of differentiation and antibody class switching [Takatsu et al. 1998]. Plasma cells, fully differentiated B cells, in nasal polyps express IL-5Ra and respond to IL-5 [Bucheit et al. 2020]. In the MATERIAL study Mepolizumab enhanced bronchial secretory IgA production [Sabogal Pineros et al. 2019]. In contrast, IL-5Ra knock-out mice show selective immunoglobulin subclass deficiencies [Yoshida et al. 1996]. Whether IL-5 blocking and IL-5Ra depleting therapies will have the same effect on B cells is uncertain. Immunological therapies can affect B cell immunoglobulin repertoires in a manner consistent with clinical activity [[name] et al. 2012].

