5.1. Research Questions

What are the actions of IL-5 and its blockade on tissue resident B cells in nasal polyps? Questions that follow include:

- Does IL-5 contribute to class-switching whether class of immunoglobulin secreted differs in the presence of IL-5 / blockade?
- Does IL-5 differentially contribute to survival of B cells expressing B cell receptors (immunoglobulins) of different classes and subclasses?
- Does IL-5 / blockade affect affinity maturation of B cells, necessary for optimal antibody responses to new and evolving pathogens?
- Are there clonotypes evident in nasal tissue of patients with nasal polyps selective for eosinophilic disease?

- Are there clonotypes evident in nasal tissue of BCR specific for putative auto-antigens (extending findings of current GSK-funded IDEA study that will be analysing BCR repertoires in blood from characterised patients)? - Do B cells expressing these clonotypes express IL-5Ra and respond to IL-5?

6. Study population

WP1: We will recruit the following:

Patients undergoing nasal polyp resections and tonsillectomy (n=10)

WP2: We will recruit to the following groups:

- Nasal polyps not on biologics (n=6)
- Nasal polyps on anti-IL-5(R) biologics (n=6)
- Control patients without nasal polyposis (n=6)

We will use purposive sampling in our recruitment of the nasal polyps not-on-biologics and control patients groups to attempt to match patient characteristics (i.e. asthma status, age and gender) to the patients with polyps on biologics, which is predicted to be the more difficult group to recruit. Control patients will predominantly be patients undergoing nasal surgery for deviated nasal septa (structural rather than immunological pathology).

Research tissue from a single patient may be used for both WP1 and WP2.

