12.2. Source Data

Source data (original data generated by study)

- Participant demographics (age and gender)
- · Medical history of eczema, asthma, allergies, rhinitis
- Clinical reason for surgery
- Medication history (topical, nasal therapy or systemic corticosteroids; biologic therapy)
- Latest blood eosinophil count, FeNO (where available)

Source documents (data not generated by study)

· Patient medical records

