13.3. Laboratory procedures

All laboratory procedures will be conducted purely for research purposes and not form part of any clinical care. Initial sample processing will be undertaken at the Blizard Laboratories, QMUL. Further pseudo-anonymised sample analyses by be undertaken by external collaborators where the assay cannot be conducted at QMUL.

Tissue samples will be dissociated by mechanical disruption. Immune cells may be isolated or enriched with magnetic beads and/or flow cytometry as per experimental protocols. Immune cells will be processed for single cell RNA sequencing using the 10X genomics platform at the genome centre core facility at the Blizard Institute. For bulk antibody repertoire analysis the tissue will be homogenized and RNA isolated from the homogenate. Antibody sequencing libraries will be generated by targeted PCR and then sequenced at the genome centre core facility at the Blizard Institute.

Subject to initial experiments being successful, B cell specificity will be interrogated using dCODE Klickmer oligonucleotide-barcoded antigens in later experiments, using antigens from viruses (e.g. covid, rhinovirus) and bacteria (e.g. Staphylococcus aureus enterotoxins [Chen et al. 2017]) known to trigger flares of nasal polyp inflammation and asthma exacerbations. dCODE oligonucleotide-barcoded putative auto-antigens,

identified as part of the ongoing GSK-funded IDEA ISS, will also be examined to compare tissue to blood B cell auto-antibody expression, and whether those B cells are IL-5 responsive.

Specific sequences will be analysed using an established computational pipeline based in the Immcantation packages (Nouri & Kleinstein. Bioinformatics 2018). Clonally-related B cell discerned by sequence identity (same VDJ gene rearrangement and CDRH3) and clonal lineages will be reconstructed. The properties of individual antibody repertoires will be analysed to quantify (per subclass) i) average clone sizes to provide a measure of clonal expansion, ii) clonal relatedness to other subclasses, and iii) frequencies of somatic hypermutation. These measures will then be compared between different patient groups (ex vivo WP) or stimulation condition (in vitro WP).

Samples may be sequenced *ex vivo* or after *in vitro* cell stimulations as described in the Study Design.

Other laboratory techniques that may be undertaken within the planned experimental work package:

- B cell flow-cytomtery
- o ELISA for immunoglobulin proteins

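### WP2 reads IL-5Ra with an antibody to a receptor that some treated patients' drug may already bind, and no check separates masking from depletion

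*Protocol*

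**What the plan says.** Protocol section 6 defines the treated WP2 group as "Nasal polyps on anti-IL-5(R) biologics (n=6"), so drugs against the cytokine and drugs against its receptor both qualify. The exclusion criteria in section 6.2 bar neither. Section 4.1 names one receptor-directed agent: "Benralizumab (that targets IL-5Ra expressing cells for cell-mediated killing").

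Section 7 (WP2) says that samples are dissociated and "cells labelled with oligonucleotide-barcoded antibodies to CD20 and IL-5Ra". The repertoire analysis then covers "tissue B cells from the three patient groups, stratified by IL-5Ra expression". No clone or epitope is given for the label.

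Section 13.3 adds that "Immune cells will be processed for single cell RNA sequencing using the 10X genomics platform", but does not say that the receptor's transcript will define or check IL-5Ra status. Section 12.2 lists "Medication history (topical, nasal therapy or systemic corticosteroids; biologic therapy") among the source data, without listing time since the last dose.

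The background explains why receptor-bearing B cells matter. Section 4.1 warns that "depletion of IL-5R expression B cells may theoretically predispose to specific antibody deficiencies", and also states: "Whether IL-5 blocking and IL-5Ra depleting therapies will have the same effect on B cells is uncertain".

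**The concern.** The variable that splits the cells is read with an antibody to the molecule that one class of treatment targets. If drug and label compete for the receptor, a surviving cell that carries drug is read as low or negative. Only patients on a receptor-directed drug are affected, so the error would be differential between groups and not random noise. Analysing each drug separately would not remove it.

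There are two consequences.

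- A masked cell and a missing cell give the same reading. The study could seem to show the depletion that the background raises as a safety question when the cells are still there.
- The immunoglobulin classes of masked cells are counted in the IL-5Ra-low stratum, which distorts the class and subclass comparison within strata.

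The question in section 5.1 of whether clonotype-bearing B cells express IL-5Ra is open to the same error.

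**Working it through.** The protocol gives no figure to reproduce, so the check has two parts: whether the planned work would reveal masking, and how large its effect could be.

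**Would the plan reveal it?**

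- Section 7 says WP1 will refine the methods for WP2. However, section 5 takes WP1 polyp tissue from donors not on biologics, and the only drug named for the WP1 cultures (sections 5 and 7) is mepolizumab, which binds the cytokine. As written, WP1 never tries the label with a receptor-binding drug present.
- The complementary bulk sequencing uses RNA from homogenised tissue (section 13.3), so it cannot recover a cell-by-cell IL-5Ra split.
- Samples are processed within 24 hours, and what is kept is processed material such as excess RNA (section 13.4). No restaining is provided for.
- Section 6 expects the treated group, six patients, to be the harder one to recruit, so lost readings would be difficult to replace.

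**How large could it be?**

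The documents give none of the following inputs, so all are assumptions shown over a range, and no true depletion is supposed:

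- *p*: true IL-5Ra-positive share of B cells (taken as 10% or 20%, equal across patients);
- *f*: fraction of those cells masked in a patient on a receptor-directed drug (0 to 1);
- *k*: number of the six treated patients on such a drug (0 to 6).

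*Step 1. One patient on a receptor-directed drug.* Apparent share = p × (1 − f). With p = 10%:

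- f = 0: 10%
- f = 0.5: 10% × 0.5 = 5%
- f = 0.9: 10% × 0.1 = 1%
- f = 1: 0%

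*Step 2. Mean of the treated group.* Apparent ÷ true share = 1 − (k/6) × f:

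| k | f = 0.5 | f = 0.9 | f = 1 |
|---|---|---|---|
| 0 | 1.00 | 1.00 | 1.00 |
| 1 | 0.92 | 0.85 | 0.83 |
| 3 | 0.75 | 0.55 | 0.50 |
| 6 | 0.50 | 0.10 | 0.00 |

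*Step 3. Contamination of the IL-5Ra-low stratum in an affected patient.* Truly positive part = p × f ÷ (1 − p + p × f):

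- p = 10%, f = 0.5: 0.05 ÷ 0.95 = 5%
- p = 10%, f = 1: 0.10 ÷ 1.00 = 10%
- p = 20%, f = 0.5: 0.10 ÷ 0.90 = 11%
- p = 20%, f = 1: 0.20 ÷ 1.00 = 20%

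So masking alone could produce anything from no apparent loss to complete apparent loss. The contamination is smaller, but could matter for an immunoglobulin class that is rare among truly negative cells.

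**The case against.** The strongest reply is that clone choice and staining controls are bench details. Section 7 names a target and not a clone, section 13.3 leaves cell isolation and enrichment to experimental protocols, and nothing prevents the laboratory from choosing a non-competing label. The documents also do not say that drug-coated B cells survive in the tissue, or that drug is still bound at surgery. The range in the working runs from no error to total error because the deciding fact is not given. All of this stands, and it makes the point a risk.

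A reader might infer more than the text supports in three ways.

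- *That WP2 sorts cells into positive and negative by the surface label alone.* Section 7 describes labelling and stratifying. It gives no sort on IL-5Ra and no cut-off, and the protocol does not rule out using the transcript; it simply does not provide for it.
- *That the primary objective is compromised.* Comparing classes, subclasses and hypermutation between groups does not need the IL-5Ra label, and neither does the bulk sequencing. Counting IL-5Ra-positive B cells is not among the objectives in section 5 or the questions in section 5.1; depletion appears as a motivating concern in the background. The study also calls itself hypothesis-generating (section 9).
- *That requiring label and transcript to agree cell by cell would settle the matter.* It would not. A masked cell whose transcript is missed is negative on both readouts, and agreement would then wrongly point to depletion.

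What the reply does not remove is that the protocol itself chose this readout, stratifies on it, admits the drugs that could interfere with it, and plans no step that would show interference. Later analysis of the label data alone could not separate masking from depletion.

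**Conclusion.** The point holds as an uncontrolled measurement risk that is cheap to remove. It applies only to treated WP2 patients on a receptor-directed drug (0 to 6 of 6), and only to the IL-5Ra-stratified analyses and the question of IL-5Ra on clonotype-bearing cells. It rests on one unstated fact, whether the label competes with bound drug, and on such drug and surviving receptor-bearing cells being present in the tissue at surgery. If the label does not compete, or if no recruit is on such a drug, there is no error. If it competes fully, the reading in those patients is 0% whatever the true share. The documents do not support saying that masking will occur, or that the main class and subclass comparison is biased by it.

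**What to change.** In section 7 (WP2):

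1. Specify an anti-IL-5Ra label shown to bind in the presence of the receptor-directed drug. One bench check during WP1 is enough: label spare cells from untreated polyps with and without pre-incubation with the drug.
2. Add the IL5RA transcript from the planned single-cell RNA data as a second, supportive definition of IL-5Ra status. Compare the transcript-positive share, by patient or by B-cell subset, between patients on receptor-directed drugs and the other groups.
3. Show results for receptor-directed and cytokine-directed patients separately, and record the named biologic and the time since the last dose.
4. State that a low surface-label share in patients on a receptor-directed drug will not be read as depletion unless the label has passed the competition check or the transcript-positive share is also reduced.

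The cost is a choice of clone, one bench check, two data items and an extra summary. The transcript step assumes that the single-cell run yields gene expression as well as BCR sequences. Its drawback is that transcript calls are sparse in single cells, so classification of individual cells will be incomplete and the transcript serves only as a group-level check. Nothing in patient care changes.
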